If there is no clear epidemiological history, they should have two or more A symptoms or one or more B symptoms and detectable SARS-CoV-2 specific IgM; or have two or more A symptoms and One or more B symptoms.

① Epidemiological history

A. Long-term residence or stay in the affected area for more than 7 days is deemed to have an epidemiological history; or

B. History of travel or residence in the community where the case was reported within 14 days before the onset of illness; or

C. In contact with SARS-CoV-2 infected or asymptomatic infected persons within 14 days before the onset; or

D. Cluster cases (2 or more cases of fever and/or respiratory symptoms occurred in a small area such as home, office, school, etc. within 2 weeks).

② Clinical symptoms

Symptoms A (last for at least 2 days): fever (axillary temperature $\geq 37.5^{\circ}\text{C}$); chills; sore throat; fatigue; nasal congestion or runny nose; body pain, muscle pain; headache; nausea or vomiting; diarrhea.

Symptoms B: Cough; new taste or smell disorders; shortness of breath or difficulty breathing; imaging features of COVID-19

Confirmed cases:

On the basis of the clarification of the suspected case, the COVID-19 PCR diagnosis is positive.

Differential diagnosis:

Encourage any possible pathogenic differential diagnosis.

Confirmed mild COVID-19 cases:

The clinical symptoms were mild, and there was no sign of pneumonia on imaging.

Confirmed moderate COVID-19 cases:

Showing fever and respiratory symptoms with radiological findings of pneumonia.

Confirmed severe COVID-19 cases:

Confirmed COVID-19 case meeting any one of the following criteria:

- Respiratory distress ($RR \geq 30$ breaths/min);
- Oxygen saturation $\leq 93\%$ at rest;
- Arterial partial pressure of oxygen (PaO_2)/ fraction of inspired oxygen (FiO_2) ≤ 300 mmHg ($1\text{mmHg}=0.133\text{kPa}$);
- The clinical symptoms progressively worsened, and the chest imaging showed $>50\%$ obvious lesion progression within 24-48 hours.

Confirmed Critical COVID-19 cases:

Confirmed COVID-19 case meeting any one of the following criteria:

- Respiratory failure and requiring mechanical ventilation;
- Shock;
- With other organ failure that requires ICU care;
- Death

We will make an interim analysis of the change of incidence, according to which the protocol will be adjusted as necessary.

Please refer to Table 1. for the sample size and procedures of the clinical trial.

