4.5. Vaccine efficacy

Research Indicators

$$\text{Vaccine efficacy} = \left(1 - \frac{\text{incidence density of vaccine group}}{\text{incidence density of placebo group}}\right) \times 100\%.$$

Incidence density during the follow-up period = (number of confirmed cases during the effective follow-up period/number of observation years of all vaccinated subjects during the effective follow-up period) × 100%. In the calculation of the number of observation years, the termination of follow-up period is considered as follows: for COVID-19 cases in the subjects, once there are confirmed cases that meet the diagnostic criteria of the "Diagnosis and Treatment Protocol for COVID-19" (the latest version), relevant data will be collected to complete follow-up; For non-cases, the follow-up of vaccine efficacy will be continued until the day of withdrawal from the study.

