7.4.8 Case Monitoring

This clinical trial adopts a monitoring modality with passive monitoring as the main approach and active monitoring as a supplement. After the subjects received the first dose of vaccine, the monitoring of COVID-19 cases will be initiated until the end of the study, and relevant information will be collected.

Passive Monitoring

Passive monitoring has two situations where subjects spontaneously report and when symptoms occur, they actively go to the hospital for treatment.

- 1) After the subjects develop symptoms, they actively report to the investigator through the hotline or email;
- 2) When the subjects visit hospital after developed symptoms, the subjects are monitored through hospital system;
 - When the subject has fever and/or respiratory symptoms that meet the definition of a suspected case, the subject should inform the investigator and go to the designated place for PCR testing;
 - If the subject visits the hospital for treatment, the investigator should arrange to collect nasopharyngeal swabs for PCR testing every 2-3 days; determine the clinical classification based on the severity and duration of symptoms, and isolate the mild and moderate cases; arrange hospitalization for severe and critical cases;
 - For non-hospitalized patients, the subjects will be followed up by remote teleconsultation and re-tested for PCR every 3 days to monitor and document the progress of the illness, medication status, symptom severity and other related information. If the subject's condition deteriorates, he needs to be sent to the hospital for timely treatment;
 - For hospitalized patients, continue to pay attention to the development of the disease, and conduct testing and examination like blood routine, blood chemistry, imaging examinations as well as other medical treatment. Closely monitor and collect evidence related to the subject's diagnosis and treatment, and record the progress of the disease, medication, and the severity of symptoms until the outcome;
 - Collect the PCR result, defined a confirmed case based on the positive result;
 - The subject is in the convalescent phase which is 3-4 weeks after the first positive PCR result. During the convalescent period, the subject's nasopharyngeal swab is collected for PCR retest

and neutralizing antibody test; if the PCR test result is positive, repeated PCR testing needs to be done once a week until the PCR result is negative.

2. Active monitoring

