- 1) Weekly teleconsultation to collect information;
- 2) Regularly monitor and collect information;

The subsequent procedures for suspected cases identified through the above two monitoring process approaches is the same as passive monitoring procedures.

Endpoint assessment or adjudication of the cases

Establish an independent case Endpoint Assessment or Adjudication Committee (EAC) composed of 3 or more local medical experts to make a final diagnosis for each case. When a case meets the etiological indicators, the diagnosis and treatment progress document, case investigation document, serology, cytokines and other lab reports will be submitted to EAC, the case can be determined as a confirmed case of COVID-19 (clinical endpoint) after a blinded review of the EAC experts. Refer to the EAC charter (Appendix 1) for details.

Case Monitoring Flowchart

[figure not shown]

Table 4. Schedule of Events

Visit number	1	2	3	4	5	6	7	8	9	10	11, 13, 14	12, 15, 18	16, 17, 19, 20	21
Day (safety visit)	D0 ☞	D3 ☞	D7 ☞	D14 ☞	D21 ☞	D24 ☞	D28 ☞	D35 ☞	D42 ☞	D49 ☞	D81 D141 D171 ☞	D111(M3) D201 (M6) ; D291 (M9) ☞	D231 D261 D321 D351 ☞	D381 (M12) ☞
Visit (window +/- days)	0d	-2d	+2d	+3d	+7d	-2d compare to V5	+2d compare to V5	+10d compare to V5	+3d compare to V5	+10d compare to V7	+3d compare to V7	+10d compare to V7	+3d compare to V7	+10d compare to V7
SCREENING/BASELINE														
Study Informed consent ¹	✓													
Inclusion/exclusion criteria evaluation	✓ ⁷				✓ ⁷									
Demographics	✓													
Medication history	✓				✓									
Measured height	✓				✓									
Review contraception ²	✓				✓									
EDC Randomization registry	✓													
TREATMENT														
Administer study drug	✓				✓									
SAFETY ASSESSMENTS														
Vital signs specifically RR, HR, BP, body temp/ O2 sat	✓				✓			✓		✓				
Body weight	✓				✓									
Physical Examination ⁶	✓ ⁶				✓ ⁶			✓ ⁶		✓ ⁶				
Post-vaccination observation at site ⁴	✓				✓									
Post-vaccination phone call	✓	✓	✓	✓	✓	✓	✓	✓	✓	✓	✓	✓	✓	✓
Concomitant medication	✓	✓	✓	✓	✓	✓	✓	✓	✓	✓	✓	✓	✓	✓
Adverse events	✓	✓	✓	✓	✓	✓	✓	✓	✓	✓	✓	✓	✓	✓
Diary Card ⁵	✓				✓					✓				
LABORATORY TESTING														
COVID-19 PCR ⁷	✓							✓ ⁷						
Pregnancy test	✓ ³				✓ ³									
Neutralizing Antibody Test	✓							✓		✓ ⁸		✓ ⁸		✓ ⁸

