9.2. Analysis sets

(1) Analysis Set for Efficacy

Full Analysis Set (FAS): includes all subjects who follow intent to treat (ITT) principle, undertake randomization, received at least one dose of vaccine and have ≥ 1 follow up for case surveillance.

COVID-19 cases included in FAS analysis: initial occurrence post first-dose vaccination and involvement in efficacy assessment in FAS analysis and COVID-19 cases confirmed by etiological and serological evidence, and deaths caused by COVID-19.

modified Full Analysis Set (mFAS): It is a subset of FAS population, and includes all subjects who take two doses of vaccination and have at least 1 follow-up for efficacy after all course immunization.

Per Protocol Set (PPS): being a subset of mFAS, the subjects in PPS are more compliant to the protocol, including all subjects who meet the inclusion/exclusion criteria, undertake randomization, receive 2 doses of vaccination according to the protocol requirements, and have ≥ 1 follow up in 14 days after the 2nd vaccination for case surveillance. Among them, subjects who meet the following conditions should be excluded from PPS: (1) they do not meet the selection criteria; (2) The subjects received the wrong vaccination or incorrect dose of vaccine; (3) For those whose vaccination time exceeds the window, the researcher, the sponsor and the statistician shall jointly agree on the time exceeding the window before unblinding; (4) any other conditions which potentially affect the evaluation of vaccine efficacy.

Confirmed COVID-19 cases included in PPS; initial occurrence after 14 days following 2-dose vaccination, involvement in efficacy assessment in data set and COVID-19 cases confirmed by etiological and serological evidence, and deaths caused by COVID-19.

(2) Analysis Set for Immunogenicity

Full Analysis Data Set (FAS): includes all subjects from immunogenicity subset who follow ITT principle, undertake randomization, receive at least one dose of vaccine, and have pre-vaccination immunogenicity data.

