9.3. Statistical Methods

(1) General considerations

Quantitative data will be described by mean, median, standard deviation, minimum and maximum. Frequency and percentage will be used to describe qualitative data and ordinal data.

All analysis will be performed by using SAS 9.4 or later version.

(2) Subject disposition and demographics

The number of subjects randomized, discontinued and completed in each group will be summarized. The discontinued subjects will be listed, including the reason for discontinuation. The number of subjects in the analysis sets will be presented as well.

The demographics of all subjects will be summarized by groups.

(3) Efficacy analysis

The number of cases of admission, dropout, elimination, blood collection, dropout reasons, combined medication and combined vaccines in the experimental and placebo groups shall be described. The percentage of dropout and concomitant medication in the experimental and placebo groups shall be compared with χ^2 test or Fishers exact test.

Protection efficacy (FAS, mFAS and PPS analysis):

The person-year incidence rate of COVID-19 after 14 days following two-dose of vaccination will be calculated in Vaccine-1, Vaccine-2 and placebo groups. Vaccine efficacy from person-year incidence rate of Vaccine-1 and Vaccine-2 with the corresponding 95% CIs will be estimated. The differences between Vaccine-1, Vaccine-2 and placebo will be compared by using Poisson regression model. The person-year incidence rate is calculated by (Number of COVID-19 cases / Person years in exposure of all subjects) \times 100%. In the calculation of person years in exposure, the start date is after 14 days following the 2nd dose. The end date is the diagnosed date of COVID-19 case for ones who are confirmed as COVID-19 cases or last follow-up date for others. Vaccine efficacy (VE)= 1-(person-year incidence in vaccine group/ person-year incidence in placebo group).

Vaccine efficacy after 14 days following two-dose vaccination will be evaluated based on mFAS and PPS. The VE from mFAS population is the primary result, and the efficacy from PPS population is a sensitivity analysis result.

Furthermore, the same statistical methods will be employed to estimate the VE after one dose based on FAS population. Kaplan-Meier plot will be used to depict the incidence of COVID-19 from FAS population.

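### Section 9.2 adds serological evidence to a case definition that is PCR-based elsewhere, gives the primary set (mFAS) no case rule, and serology reaches a blinded adjudication without stated masking

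*Protocol*

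**What the plan says.** **Confirmation by PCR.** The case definition in section 4.2, repeated in the synopsis, reads: "On the basis of the clarification of the suspected case, the COVID-19 PCR diagnosis is positive". Section 7.4.8 agrees: "Collect the PCR result, defined a confirmed case based on the positive result".

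**Serology in the analysis sets.** Section 9.2 describes the cases that count in FAS, and again those that count in PPS, as "COVID-19 cases confirmed by etiological and serological evidence, and deaths caused by COVID-19". It names no assay, titre, rise or sampling time. mFAS is defined as a population only, with no statement of which cases count. Yet section 9.3 says "The VE from mFAS population is the primary result", with PPS as the sensitivity analysis and FAS used for efficacy after one dose.

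**Serology in the suspected-case step.** For subjects without clear epidemiological history, one route in 4.2 requires "two or more A symptoms or one or more B symptoms and detectable SARS-CoV-2 specific IgM". The other route without such history needs symptoms from both lists and no IgM.

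**Serology at adjudication.** Section 7.4.8 sends the EAC a file in which "serology, cytokines and other lab reports will be submitted to EAC", ahead of a review that it describes as blinded. It refers to an EAC charter (Appendix 1), which is not shown.

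**End of follow-up.** Section 4.5 closes a case's follow-up "once there are confirmed cases that meet the diagnostic criteria of the" latest version of an outside diagnosis and treatment guideline, not the protocol's own 4.2 definition.

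**The concern.** The trial is event-driven: each vaccine-placebo comparison is read at 50, 100 and 150 cases. What counts as a case therefore fixes both the estimate and the date of each analysis. A PCR rule and a PCR-plus-serology rule can give different counts from the same data, and the protocol does not settle which one feeds the primary analysis.

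Serology is an awkward second condition in this trial because the vaccines are meant to raise the antibodies being measured. An infected vaccinee and an infected placebo recipient need not have the same chance of meeting a serological criterion, least of all one that is not written down. If the chances differ, vaccine efficacy (VE) is biased through case counting alone.

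An EAC that sees antibody results also holds some information about allocation, which weakens the protection that blinded review is meant to give.

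**Working it through.** **1. The passages side by side**

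| Place | Case rule | Serology needed to confirm? |
|---|---|---|
| Synopsis, 4.2 | Suspected case plus positive PCR | No |
| 7.4.8 | Positive PCR, then EAC review | No, but it is in the EAC file |
| 9.2, FAS | Etiological and serological | Yes, as worded |
| 9.2, mFAS (primary) | None stated | Unclear |
| 9.2, PPS | Etiological and serological | Yes, as worded |

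By 9.2, PPS is a subset of mFAS and mFAS a subset of FAS. The primary set thus lies between two sets that both carry the serological wording. There are two readings:
- mFAS inherits the wording. The primary endpoint then contradicts 4.2.
- mFAS follows 4.2. The PPS analysis then differs from the primary one in endpoint and population together, so a difference between them could not be attributed to protocol compliance.

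Neither reading can stand without a correction.

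**2. The plan's own figures**

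Inputs from 9.4.1: 150 cases per pair, VE 0.6, lower limit 0.3, placebo incidence 0.0085 a year, 1:1:1 allocation, 15% drop-off. From 9.5: 5% two-sided error, so 0.025 one-sided, with 0.0231 at the final look.

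- N per group = 150 / [(1 + 1 − 0.6) × 0.0085] = 12,605. Total = 12,605 / 0.85 × 3 = 44,488. Both agree with 9.4.1.
- Given 150 cases and equal person-time, the vaccine-arm count is binomial with p = (1 − VE) / (2 − VE). At VE 30%, p0 = 0.7/1.7 = 0.412. At VE 60%, p1 = 0.4/1.4 = 0.286.
- Normal approximation to power at 0.025: Φ{[p0 − p1 − 1.96√(p0(1 − p0)/150)] / √(p1(1 − p1)/150)} = 90.0%.
- Exact binomial: success needs 49 or fewer vaccine-arm cases. P(X ≤ 49) = 0.0200 under p0, and P(X ≤ 50) = 0.0298 is too large at either 0.025 or 0.0231. Power under p1 is 88.4%.

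The stated 90% is reproduced.

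**3. What unequal counting would do**

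Let r be the proportion of PCR-confirmed cases that also meet the serological condition in the vaccine arm, divided by the same proportion on placebo. The documents give no value, so r is an assumption. Apparent VE = 1 − (1 − true VE) × r. The cut-off stays at 49 of 150, and only the final look is considered.

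| r (assumed) | True VE 30%: apparent VE | Type I error | True VE 60%: apparent VE | Power |
|---|---|---|---|---|
| 0.80 | 44% | 23.1% | 68% | 99.3% |
| 0.90 | 37% | 7.7% | 64% | 96.3% |
| 0.95 | 33.5% | 4.0% | 62% | 93.1% |
| 1.00 | 30% | 2.0% | 60% | 88.4% |
| 1.05 | 26.5% | 1.0% | 58% | 82.1% |
| 1.10 | 23% | 0.4% | 56% | 74.4% |
| 1.20 | 16% | 0.1% | 52% | 56.3% |

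Example, r = 0.90 at true VE 30%: p = 0.63/1.63 = 0.387, and P(X ≤ 49) = 0.0765.

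The table shows sensitivity. It is not an estimate of what will happen.

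**The case against.** The best defence is that PCR is the operative test throughout. Every confirmed case needs it, and files go to the EAC only once the etiological criterion is met. The 9.2 phrase may then be a loose description of laboratory confirmation. It is also attached to FAS and PPS, not to the primary set. This is fair, and it is why the primary rule can be called unclear but not plainly serological. It does not remove the conflict, because the phrase appears twice and mFAS is left without a rule.

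Four stronger readings are tempting and are not supported:

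- **That cases are counted differently by arm.** Nothing in the protocol requires an antibody rise, and r could lie on either side of 1. A reader might use the 9.4.2 planning rates for a 4-fold IgG rise (10% on placebo, 10% + 30% = 40% on vaccine). Those are hypothetical responses to immunization. They do not describe PCR-positive patients, in whom infection itself can raise antibody in any arm.
- **That the EAC is unblinded.** Even if those rates are borrowed, with VE 0.6 and 1:1:1 allocation, the probability that a case is in a vaccine arm moves from 0.8/1.8 = 44% to 0.32/0.42 = 76% with a positive result, or to 0.48/1.38 = 35% with a negative one. Neither identifies the arm. The charter may already mask these results.
- **That the IgM route lets antibody create cases.** It applies only without epidemiological history, which more than 7 days in an affected area supplies, and section 8.2 reports many patients at each site. PCR is still required. The route may rarely decide a case.
- **That the outside guideline in 4.5 changes the primary count.** The clause governs the end of follow-up, and 9.3 separately ends person-time at diagnosis. At 0.85% incidence a year the effect on person-time is negligible. It is a matter of consistency.

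Nor is the one-case step between 49 and 50 a defect, since any discrete cut-off has one. At VE 60% about 150 × 0.4/1.4 = 43 vaccine-arm cases are expected, six below the limit.

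**Conclusion.** The point holds as an inconsistency in the definition of an efficacy case. Sections 4.2 and 7.4.8 use PCR, 9.2 adds undefined serological evidence for FAS and PPS, and the primary set has no rule. In a trial of antibody-inducing vaccines, a serological condition cannot be presumed neutral between arms.

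No bias is demonstrated, and its direction is open. The illustration rests on assumed values of r, equal person-time and the final look alone. On those terms, counting vaccine-arm cases at 0.90 of placebo raises the exact type I error from 2.0% to 7.7%, while r = 1.10 lowers power at VE 60% from 88% to 74%.

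Serology in the EAC file is a secondary weakness: informative about the arm, not decisive, and possibly covered by the charter.

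This should be fixed before unblinding, because a case rule chosen afterwards could be suspected of following the results.

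**What to change.** 1. **Section 9.2.** Replace the reference to etiological and serological evidence with the 4.2 definition (suspected case plus positive RT-PCR, confirmed by the EAC), and state that it applies to FAS, mFAS and PPS.
2. **Section 7.4.8 and the EAC charter.** Withhold or mask antibody results in the file that the EAC reviews. If the charter already does this, say so in 7.4.8.
3. **Section 4.5.** Refer to the same 4.2 definition for the end of follow-up.
4. **IgM route.** Keep it in 4.2, since deleting it would change which cases are captured. Add a sensitivity analysis that leaves out cases that qualified as suspected only through IgM.

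The cost is wording in the protocol and charter, plus one extra analysis. The EAC loses serology as supporting evidence, which is a small downside. The 150 cases, the stated 90% power, 12,605 per group and 44,488 in total are unchanged.

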9.3. Statistical Methods

(1) General considerations

Quantitative data will be described by mean, median, standard deviation, minimum and maximum. Frequency and percentage will be used to describe qualitative data and ordinal data.

All analysis will be performed by using SAS 9.4 or later version.

(2) Subject disposition and demographics

The number of subjects randomized, discontinued and completed in each group will be summarized. The discontinued subjects will be listed, including the reason for discontinuation. The number of subjects in the analysis sets will be presented as well.

The demographics of all subjects will be summarized by groups.

(3) Efficacy analysis

The number of cases of admission, dropout, elimination, blood collection, dropout reasons, combined medication and combined vaccines in the experimental and placebo groups shall be described. The percentage of dropout and concomitant medication in the experimental and placebo groups shall be compared with χ^2 test or Fishers exact test.

Protection efficacy (FAS, mFAS and PPS analysis):

The person-year incidence rate of COVID-19 after 14 days following two-dose of vaccination will be calculated in Vaccine-1, Vaccine-2 and placebo groups. Vaccine efficacy from person-year incidence rate of Vaccine-1 and Vaccine-2 with the corresponding 95% CIs will be estimated. The differences between Vaccine-1, Vaccine-2 and placebo will be compared by using Poisson regression model. The person-year incidence rate is calculated by (Number of COVID-19 cases / Person years in exposure of all subjects) \times 100%. In the calculation of person years in exposure, the start date is after 14 days following the 2nd dose. The end date is the diagnosed date of COVID-19 case for ones who are confirmed as COVID-19 cases or last follow-up date for others. Vaccine efficacy (VE)= 1-(person-year incidence in vaccine group/ person-year incidence in placebo group).

Vaccine efficacy after 14 days following two-dose vaccination will be evaluated based on mFAS and PPS. The VE from mFAS population is the primary result, and the efficacy from PPS population is a sensitivity analysis result.

Furthermore, the same statistical methods will be employed to estimate the VE after one dose based on FAS population. Kaplan-Meier plot will be used to depict the incidence of COVID-19 from FAS population.

The same statistical methods as above are used to evaluate VEs against severe cases of COVID-19 and deaths accompanied by COVID-19.

(4) Immunogenicity analysis (FAS and PPS analysis):

Statistical description: The antibody titer should be logarithmically transformed. Minimum value, maximum value, median and quartile spacing, GMT and 95% CI should be shown.

Comparison of antibody levels before immunization: Logarithmic conversion was carried out on antibody titers, and two independent sample T tests (normal and homogeneous variance) or corrected T tests (normal but uneven variance) shall be used to compare the GMT of neutralizing antibodies against COVID-19 before immunization between the experimental and placebo groups with various ages.

Comparison of antibody levels after immunization:

- ✓ calculate the antibody 4-fold increase rate and 95% CI of anti-SARS-CoV-2 antibody in the experimental and placebo groups with various ages after immunization, and make superiority comparison. If the lower limit of 95% CI of antibody 4-fold increase rate is $\geq 10\%$, the superiority hypothesis is valid;
- ✓ calculate 95% CI of GMT ratio of anti-SARS-CoV-2 antibody in the experimental and placebo group after immunization. If the lower limit of 95% CI ratio is ≥ 1.1 , the superiority hypothesis is valid;
- ✓ calculate the GMI and 95% CI of anti-SARS-CoV-2 antibody in the experimental group after immunization.

(5) Safety analysis (SS analysis)

Describe the frequency and number and incidence of adverse reactions/events. If a subject manifest the same adverse reaction/events repeatedly, the description on this adverse reactions/events should indicate the most severity, the closest relationship with vaccination and the earliest starting time. However, in the list of adverse reactions/events, all adverse reactions/events will be listed.

Using χ^2 test or correct χ^2 test or Fishers exact test, the incidence of total adverse reactions, systemic adverse reactions, local adverse reactions and unexpected adverse reactions in the experimental and placebo groups within 30 minutes, 0-7 days and 8-28 days after inoculation of each dose were compared χ^2 test or correct χ^2 test or Fishers exact is used to compare the difference of SAE incidence rate between the experimental and placebo groups within 360 days after the whole inoculation. The rank sum of two independent samples is used to compare the average grade of adverse reactions in the experimental and placebo groups.

In the analysis of adverse events/reactions stratified by symptoms and SAE, MedDRA coding is used to carry out comparative analysis of SOC level and PT level respectively.

